7.1 Data collection

Please check the data source that is applicable to your study, more may apply:		
Data will be prospectively collected (data/ biomaterials from [some] participants will be collected)		
Data will be collected from (electronic) patient records (e.g. 'EPD UMCG')		
Data will be collected from an already existing bio- or databank		
Data will be collected from a previous study (e.g. 'FAIR data' - internal/external).		
7.2 Informed consent procedure		
7.2.1 Participants will be asked informed consent	Yes  If yes: please complete 7.2.2 and 7.3.	No  If no: please complete 7.2.3 and 7.3.
7.2.2 If consent is asked complete this section		
7.2.2.1 if the potential participant is a patient:		
First contact with potential participant is made by the treatment provider, either by accompanying letter or in person.	Yes 	No 
Informed consent procedure, including signing the IC, will be carried out by the researcher/ research nurse (not the treatment provider).	Yes 	No 
7.2.2.2 For participants that are either patients or non-patients:		

• Recruitment:
 
Potential participants can register via a custom public survey URL: https://redcap.link/trajectnieuwkomers. This link is shared by organizations such as UAF, COA, and municipalities with their clients. Until now, participants who signed up were asked to provide consent for the processing and storage of their personal data for a maximum of four years. In addition, they could consent to the processing and storage of other data they provided for up to six years (after four years anonymized) for research purposes to analyze how well the trajectory fits the participant and to identify areas where newcomers may need additional support (Appendix 4).
 
With the start of this study, participants who register will:
 
 1 Be asked to provide consent for the processing and storage of personal data for up to four years to determine their eligibility for participation in the trajectory. 2 Receive the attached participant information letter and be asked to digitally sign the consent form, granting permission to use their data for research purposes, the analyses as intended within this study. 
Although the 49 participants already enrolled have previously provided consent for the prospective storage of their data, they will be asked again to provide consent for the use of their data for research purposes. This seems justified by the societal and scientific value of these outcomes as analyzing these data may help optimize the trajectory for future participants in other hospitals and improve the chances of successful integration for nursing newcomers. Only the data of participants who provide this additional consent will be used to determine the
		


results for the primary outcome measure. The number of participants who do not provide consent will also be recorded.
 
For the first analysis of the secondary outcome measures, the UMCG project coordinator invited 17 participants to contribute. These participants completed a survey, developed jointly by Regioplan and UMCG and were asked to participate anonymously (Appendix 7).
			

• Information provision:
 
The participant will only be contacted via telephone if they have given prior permission for this:
	
NA
 	
Yes
 	
No
 

Contact via telephone only serves to provide additional information, it cannot be used to ask informed consent:
	
NA
 	
Yes
 	
No
 

If either of the above 2 items are answered with 'no' please elaborate on the reason for this:
 
NA
			

• Time to consider:
 
The participant will have at least 14 days to consider participation:
	
Yes
 		
No
 

If this is not the case please describe the reason for this and what time is allotted for the participant to consider participation.
 
NA
			

• Informed consent recording:
 
Informed consent will be recorded either on paper via signature or electronically:
	
Yes
 		
No
 

If no, please elaborate on how will the informed consent be recorded?
 
NA
			

• Use of templates
 
Have the UMCG templates been used for both DIF and IC-form:
	
Yes
 		
No
 

7.2.3 If consent cannot be asked please complete this section:
			

Total number of participants who will not be asked informed consent: NA
 
Total number of UMCG participants who will not be asked informed consent: NA
			

Which WGBO argumentation applies to your study (see SOP Obtaining Informed Consent nWMO):
			

• Asking permission is reasonably impossible, because it would burden the patient to such an extent that it might cause psychological distress.
			

• Asking permission is reasonably impossible, because a large part of the participant group is likely deceased or cannot be located.
			

• Consent cannot be required because obtaining it would entail a disproportionate amount of time and effort, such as in the case of large numbers of patients or patients who were treated a long time ago
			

• Consent cannot be required because requesting consent would lead to selective response, thereby potentially biasing the research results
			

• Consent cannot be required, because:
 
NA
			

Required: In addition to the broad categories above, please clarify why these arguments apply to your specific study: NA			
The objection registry will be checked in case one or more UMCG patients will not be asked informed consent, the data from those who objected will be excluded from the analyses.		NA 	Yes 

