3.1 Introduction and rationale

The increasing shortage of nurses in the Netherlands significantly impacts healthcare capacity¹. Currently, half of all job vacancies in the Netherlands are in healthcare, trade, and business services². Reports indicate that nursing faces the largest labor market shortages among the healthcare professions, with 10,500 vacancies in 2021 and an expected 24,900 by 2031^{3,4}. Enhancing personnel inflow is one of the solutions. In that regard, the Dutch system does not appear to be well-equipped to support the integration of refugees and migrants certified as nurses in their country of origin, into healthcare positions. Recognition of qualifications is characterized by long delays and there is a lack of guidance^{5,6}. In practice, it also takes a considerable amount of time to reach a sufficient level of language proficiency, especially if individuals are unable to work and have limited exposure to the Dutch language. This slows down the speed at which the tests for obtaining a declaration of professional competence, required for Dutch healthcare licensure, are completed. Consequently, many qualified newcomers in healthcare are either underemployed or unemployed⁵. In 2022, the UMCG assessed the interest among nursing newcomer in the Northern region to participate in a fast-track integration programme (Appendix 1). As sufficient interest was confirmed, such a programme was developed that includes a vocational language and intercultural communication course, after which participants begin working as assistant nurses, salaried as care assistants, while receiving guidance toward BIG registration before taking the examinations required for BIG registration (appendix 2). In this process, data were prospectively collected on whether the participating newcomers successfully completed the different phases of the program, the duration of these phases, and the stage of integration and employment situation from which they entered, and consent was obtained from participants to store these data (appendix 3). The programme was initially developed at the UMCG and grew into a multicentre initiative. In collaboration with Healthcare of the North ('Zorg voor het Noorden', ZvhN), a regional network across the three northern provinces, it has expanded to four non-academic hospitals. As this improvement process, which was not initially conceived as a research project, appeared to be successful, it was subsequently decided to analyze the outcomes in a scientific manner. The primary objective is to determine the proportion of participants who are either progressing as planned or successfully completed the program. In addition, a qualitative analysis and a societal business case is conducted to identify where the benefits lie, thereby providing guidance for sustainable implementation once philanthropic funding is phased out. Additionally, the study aims to analyze potential racial microaggression in the workplace.

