The primary outcome: the proportion of participants who either progressed as planned, successfully completed the program by obtaining a (conditional) certificate of professional competence, or transitioned to employment as care assistants.

Secondary outcomes include:

- a societal business case and a qualitative analysis to assess the impact of the program on participants and departments
- the influence of competencies on the need for additional guidance
- potential unconscious and conscious racial microaggression in the workplace

Factors considered as potential confounders are:

- sociodemographic characteristics: age, gender, time since arrival in the Netherlands, and family situation
- educational and professional background: level and type of nursing qualification, years of work experience, and previous additional training
- language and cognitive capacity: baseline Dutch and English proficiency, learning capacity as assessed by the study skills test, and motivation and initiative
- programme-related/contextual factors: hospital/department, differences in mentorship/guidance during integration, regional labor market demand, adaptations or optimizations implemented within the program over time

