6.5 Statistical and/or qualitative analysis			
Please specify Statistical Analysis Plan (SAP): a. Description of study population: The study population consists of nursing newcomers who are already enrolled or will enrol in the fast-track integration trajectory at UMCG and participating partner hospitals. This includes both asylum seekers and migrants. Demographic and baseline characteristics include age,			

gender, language proficiency, participant status (asylum seeker or migrant), and socioeconomic and employment background. Participants who provide consent for research purposes will be included in the analysis.

b. Description of preparation of the data for analyses:

Collected data will be pseudonymized and direct identifiers removed. Data cleaning will involve checking for completeness, consistency, and plausibility. Variables will be coded according to pre-specified categories (e.g. employment history, language level). Missing data will be handled using appropriate methods such as multiple imputation or sensitivity analyses, depending on the extent and pattern of missingness. For qualitative data from surveys or interviews, responses will be anonymized and transcribed for coding and thematic analysis.

c. Specify all applicable statistical and/ or qualitative methods. This usually requires an extensive description of the planned analyses and covariates:

Primary outcome analysis: Descriptive statistics and inferential analyses (e.g. proportions, means, standard deviations) will be calculated for successful trajectory completion, BIG registration achievement. Associations with baseline characteristics will be explored using logistic regression or other appropriate multivariable models.

Secondary outcome analysis: Qualitative data from the Regioplan survey will be analyzed using thematic analysis to identify patterns, facilitators, and barriers in the trajectory. Quantitative secondary measures (e.g. language progress, employment outcomes) will be summarized using descriptive statistics and, where appropriate, tested with regression models to explore predictors of success.

Subgroup analyses will consider variables such as asylum seeker vs. migrant status, age groups, gender, and baseline language proficiency.

d. Clarify how this analysis plan, study setup, sample size and design will answer the study questions:

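### The 49 participants already enrolled count in the primary proportion only if they consent again after entry; if leavers sign less often, the success proportion is biased upward, and no bounds are planned

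*Protocol*

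**What the plan says.** The primary outcome in section 3.2 is "the proportion of participants who either progressed as planned, successfully completed the program by obtaining a (conditional) certificate of professional competence", or moved into work as a care assistant. Section 6.1 records premature exit and dropout as separate statuses, so a person who left without such a move counts against success.

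On who is counted, section 7.2.2.2 begins "Although the 49 participants already enrolled have previously provided consent for the prospective storage of their data" and goes on to say that they will be asked again, this time for research use. It then states that "Only the data of participants who provide this additional consent will be used to determine the" results on the primary outcome. Section 6.5a has the same rule: "Participants who provide consent for research purposes will be included in the analysis". About the others it says only this: "The number of participants who do not provide consent will also be recorded".

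People who register after the study starts are asked for research consent at registration, before they have any outcome.

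Section 6.5b has a general sentence on incomplete data: "Missing data will be handled using appropriate methods such as multiple imputation or sensitivity analyses, depending on the extent and pattern of missingness". The subgroups listed in section 6.5c are asylum or migrant status, age, gender and baseline language. Consent route is not among them.

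**The concern.** The two groups enter the analysis differently. For someone who signs at registration, consent cannot depend on how the programme went. For the 49 it can, because they are asked after entry. Those who left may be harder to reach or less inclined to sign, and each leaver who does not sign drops out of both the count of failures and the denominator. The main result of this descriptive study is one proportion, and a reader could not tell how far it depends on who signed.

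Two details could make early leavers harder to reach, although neither proves it. Appendix 3 says the first questionnaire asked for storage for at most one year, while section 7.2.2.2 describes up to four years until now; these passages need to be reconciled. Both telephone-contact items in section 7.2.2.2 are marked as not applicable.

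**Working it through.** **Inputs from the protocol.** Existing participants: 49 (7.2.2.2). Expected additions from March 2025: 98 in the North and 80 in the Randstad (6.3). Target total: 159 to 227 (6.2). Item d of 6.5 gives another projection, about 300; I use 6.2 and 6.3 because their arithmetic can be followed.

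**The plan's own figure.** 49 + 98 + 80 = 227, and 0.70 × 227 = 158.9, or 159. Both limits reproduce. The 49 are 49/227 = 21.6% or 49/159 = 30.8% of the final total.

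**Timing.** The language course takes about 3.5 months and the three hospital phases 14 to 20 months (Appendix 2), so the trajectory takes about 17.5 to 23.5 months. Recent entrants among the 49 may therefore have only an interim status. Being on track already counts as success; having dropped out is a known outcome.

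**Assumptions (not in the protocol).** True success p of 60% to 90%; consent c_s = 95% among successes; consent c_f = 50%, 70% or 95% among leavers.

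**Formula within the 49.** Observed proportion = p·c_s / (p·c_s + (1 − p)·c_f). For p = 0.75 and 95%/50%, there are 36.75 successes and 12.25 leavers: 34.9 / (34.9 + 6.1) = 85%, or +10 points. With 95%/70% it is 34.9 / (34.9 + 8.6) = 80%, or +5 points.

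**Formula in the final total N.** Pooled proportion = [(N − 49)·p + 49·p·c_s] / [(N − 49) + 49·(p·c_s + (1 − p)·c_f)]. This assumes that all later participants are counted and share the same p. For p = 0.60, N = 159 and 95%/50%: (66 + 27.9) / (110 + 37.7) = 63.6%, or +3.6 points.

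| True success | Bias in the 49, 95%/50% | Bias in the 49, 95%/70% | Equal consent | 95%/50%, N = 159 | 95%/50%, N = 227 |
|---|---|---|---|---|---|
| 60% | +14.0 | +7.1 | 0 | +3.6 | +2.5 |
| 70% | +11.6 | +6.0 | 0 | +3.1 | +2.1 |
| 80% | +8.4 | +4.4 | 0 | +2.3 | +1.6 |
| 90% | +4.5 | +2.4 | 0 | +1.3 | +0.9 |

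**What the recorded count allows.** With s successes among consenters and k non-consenters, the bounds over all 49 are s/49 and (s + k)/49, so their width is k/49: 5 non-consenters give 10 points and 10 give 20 points. Example on assumed counts: 39 successes and 10 leavers, of whom 5 leavers do not sign. The true proportion is 39/49 = 79.6%. Consenters alone give 39/44 = 88.6%. The bounds are 39/49 = 79.6% and 44/49 = 89.8%, which contain the true value.

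**The case against.** The strongest reply is that the inclusion rule is a consent requirement and not an analytic choice: data from people who have not agreed to research use cannot be analysed. That stands, and the point does not ask for anything else. It concerns what is reported beside the consenters' proportion.

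A second reply is that bounds are a sensitivity detail, that 6.5b already names sensitivity analyses, and that a separate SAP may use the recorded count. Part of this stands: no use is stated, but none is excluded. Yet the rule that creates the risk is fixed in the protocol, and the sentence in 6.5b is general and does not address people left out for lack of consent.

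Third, section 3.2 lists programme changes over time as a confounder and section 4.2 ticks both retrospective and prospective, so differences between early and late participants are recognised. Neither amounts to a split by consent route.

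Three stronger readings are tempting, and the protocol does not support them:

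- A reader might infer that the 49 were picked because they did well. Section 3.1 says only that the programme "appeared to be successful, it was subsequently decided to analyze the outcomes in a scientific manner". Apparent success prompted the analysis; nobody was selected on outcome.
- A reader might infer that the outcome of all 49 is known when they are asked. Some may still be in progress.
- A reader might infer that leavers are known to consent less often. That is a risk, not a documented fact. People who give up the route to registration but work as care assistants count as successes, so they are not the missing failures.

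Nor does it follow that statements on performance should rest on prospective consenters alone. If the 3-year analysis is counted in calendar time from programme start, which section 3.3 does not make explicit, it would rest mainly on the 49, and such a rule would leave little to report.

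**Conclusion.** The point holds as a risk of upward bias that the plan creates and leaves unquantified. The direction follows by arithmetic whenever leavers re-consent less often than the others; with equal consent there is no bias, and with the reverse pattern it would be downward. The size rests on assumed consent rates and success proportions. Within the 49, a marked difference in consent (95% against 50%) gives about 4.5 to 14 points and a moderate one (95% against 70%) about 2.4 to 7 points. The bias matters most for an early analysis that rests mainly on these people. In the final total the marked case falls to about 0.9 to 3.6 points, if later participants are all counted and have the same true success. It should be dealt with, but it does not invalidate the study.

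**What to change.** Add to section 6.5c that, at each analysis:

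1. Beside the consenters' proportion, two bounds are reported with all 49 in the denominator: one counting every non-consenter as a non-success, one counting every non-consenter as a success. The count already recorded under 7.2.2.2 is enough.
2. The primary proportion is reported separately for the re-consented members of the 49 and for those who consented at registration, as well as pooled.

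This takes a few lines of text and two extra table rows. It needs no further personal data and respects refusal. The price is a wider reported range: about 2 points for each non-consenter among the 49 (1/49). The bounds show how much the result could depend on non-consent; they do not correct the bias.

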7.3 Linking with (other) bio-/databank			
In case the data will be linked with a /another bio-/databank, informed consent will be/has been obtained for this linkage(s)		Yes, consent 	No consent 
		Data will not be linked 	

8. Only complete in case of collaboration with parties outside of the UMCG (also called: third parties)

8.1 Which party is in the lead?	UMCG 	Not the UMCG 
8.2 Is the leading party a commercial party?	Yes 	No 
8.3 Only complete if UMCG is not in the lead: Is the role of the UMCG limited to supplying data?	Yes 	No 
8.4 Description of the cooperation 
This study involved collaboration with two external parties: Regioplan and Social Finance NL. The philanthropic organization Golsdschmeding Foundation commissioned Regioplan to perform a qualitative analysis and Social Finance NL to perform a cost-benefit analysis. For these purposes, UMCG provided anonymous participant data, including socioeconomic and employment background at the start of the trajectory, participant status (asylum seeker or migrant), age, gender, and language proficiency.
 
Additionally, the UMCG project coordinator invited 17 participants to contribute to a qualitative analysis of the trajectory. These participants completed an anonymous developed jointly by Regioplan and UMCG (Appendix 7). All data collection and handling were performed in accordance with GDPR requirements and a code of conduct established by Regioplan as co-founder and member of the Association for Policy Research (VBO) in collaboration with MOA and VSO for policy research compliance. Regioplan is also certified according to the latest ISO 9001:2015 standard and conducts regular internal and external audits to ensure quality and identify improvements.
 
For future analyses in addition to the existing contracts between the Golschmeding Foundation and Regioplan and Social Finance NL, a research data transfer agreement will be established between UMCG and the external partners (Regioplan and Social Finance NL) to regulate the use, transfer and storage of study data.
		
8.5 Data and/or biomaterial management in combination with the partners Please elaborate on the following aspects: 
 Which data (and/or biomaterials) will be shared with the partners 		

Only anonymized participant data will be shared with the partners including socioeconomic and employment background, participant status (asylum seeker or migrant), age, gender and language proficiency. No direct identifiers are shared.

- How is the data (and/or biomaterials) saved and/or destroyed after study end.

After the study ends, all shared data remain pseudonymized and are securely stored according to UMCG data management policies. Direct identifiers are either removed or securely destroyed. Access to the pseudonymized data is restricted to authorized study personnel. Any data shared with partners are either returned or securely deleted according to the research data transfer agreements

8.6 With Informed consent Please complete only if patients are asked for Informed Consent:		
In case of collaboration with commercial/for-profit organizations. Has the research participant been informed in the DIF, or will they be informed, about the collaboration with commercial third parties.	Yes 	No 
Has or will informed consent be(en) obtained for data sharing with the third party?	Yes 	No 
8.7 Contracts For both with informed consent and without informed consent: will you contact the loket Contract Research to arrange the proper contracts?	Yes 	No 
8.8 Data Protection Impact Assessment (DPIA) Will a DPIA be drawn up?	Yes 	No 
If a DPIA will not be drawn up please elaborate on the reason for this: A DPIA will not be performed as the processing of personal data in this study does not involve a high risk to the rights and freedoms of participants. This is based on the measures already implemented including pseudonymization of data once all required information is collected, temporary and limited access to direct identifiers by the study coordinator and strict access control for the Principal Investigator and authorized study delegates.		

9. Data Management Plan (DMP)

In this study the data will be collected, processed, and archived in accordance with the General Data Protection Regulation (GDPR) and the FAIR (Findable, Accessible, Interoperable, Reusable) principles under the responsibility of the Principal Investigator, as is required by the GDPR law. Please note that completion of this section is *required*. A separate DMP will not be reviewed.

